8. STUDY LIMITATIONS

There are some limitations inherent in the study design. The patient sample may not be fully representative of patients typically prescribed TROBALT. This limitation will be addressed to the extent possible by asking the prescriber to invite up to 10 consecutive patients for whom TROBALT has been prescribed. However, the neurologists may have access to patients likely to have greater knowledge of the risks associated with TROBALT due to referral from a health care provider regularly prescribing TROBALT and aware of the ongoing study and its aims.

The patients from Germany who are included in the survey may not be representative of the total epilepsy patient population using TROBALT in Germany, since new users will only be available after May 31, 2012 by re-import, requiring justification by the prescribing physician.

The physicians who are recruited to invite their patients will be a random sample of prescribers who were mailed a letter containing the language from the Physician's Guide. Prescribers will be identified as a proportionate random sample stratified by country. The sample of prescribers asked to invite their patients will be an independent sample separate from the sample of prescribers asked to complete the survey themselves.

Another potential limitation of the study is whether or not the patient has (ever) read the PIL prior to the survey. The patient will not be provided with the PIL during the survey administration, unless by chance they happen to have it with them when taking the survey. Therefore, each patient's knowledge of the risks of TROBALT is based on his/her overall experience which may or may not include the PIL, in addition to other sources of information. Various questions have been included in the survey to try and elicit the role of the PIL in the patient's knowledge of the risks associated with TROBALT, but the responses may be subject to recall bias.

The sample of neurologists who are invited to participate will be a random sample of all neurologists who received the Physician's Guide for TROBALT. The sample of participating neurologists will be self-selected since respondents will voluntarily respond to the invitation to participate; however, the survey recruitment strategies are intended to recruit a heterogeneous sample of prescribers for participation. For Germany, as noted in section 3.2.1, TROBALT will no longer be available for new patients and so only neurologists who continue to have patients on TROBALT in November 2012 will be targeted.

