- 1) 250 patients recruited from across the following countries (United Kingdom, Sweden, Denmark, Switzerland, Spain, Slovakia and Norway) and up to 100 patients from Germany who are currently using or have filled a prescription for TROBALT at least once in the last 3 months.
- 2) 200 neurologists who have prescribed an anti-epileptic drug (AED) at least once in the last 3 months, and who were on the list to which a letter containing the Physician's Guide for TROBALT was distributed from across the following countries (United Kingdom, Sweden, Denmark, Switzerland, Spain, Slovakia and Norway). At least 75 of the neurologists will have prescribed TROBALT. The survey will also aim to include up to 100 neurologists from Germany of which approximately 50 will have prescribed TROBALT.

Patients eligible for the survey will be asked to take the survey online or via a telephone interview if the latter is preferred. Neurologists will be invited to take the survey online.

The selected countries were the first five countries to launch TROBALT (Germany, Denmark, United Kingdom, Switzerland and Sweden) and an additional three countries with launch in 2011, but with relatively high rates of uptake of TROBALT (Spain, Slovakia and Norway). The selection of countries includes Switzerland, which is not part of the European Union. However, the key messages regarding the risks with TROBALT are in alignment. The rationale for surveying the first five countries to launch is so that any issues identified from these countries regarding the effectiveness of the Physician's Guide and PIL in communicating the risks of TROBALT can be addressed as soon as possible, and the key messages can be revised in a timely manner. In addition, these countries are likely to provide the greatest number of neurologists with experience of prescribing TROBALT, and their patients.

Study Endpoints/Assessments

The primary outcome of the survey is the proportion of patients/neurologists providing correct responses to a series of questions concerning the significant risks associated with TROBALT. The risks evaluated will be those described in the TROBALT PIL and in the Physician's Guide.

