3. INVESTIGATION PLAN

3.1. Study Design

This study is sponsored by GlaxoSmithKline (GSK), and will be conducted by [REDACTED] an international research consultancy.

This is a cross-sectional study of physicians' and patients' understanding of the significant risks associated with TROBALT.

Physicians will be recruited by selecting a random sample of neurologists from lists provided by GSK in each country. The list includes names of all potential TROBALT prescribers who were mailed an introductory letter including the Physician's Guide for TROBALT (Appendix 1). Following recruitment, neurologists' understanding of the potential risks associated with TROBALT will be evaluated using an online survey. Each invitation will include information on how to access the survey on-line, and will include a unique code to ensure that the invitation is used only once.

The primary method of recruiting patients is through their physicians. In countries in which a list of current TROBALT prescribers can be obtained, a random sample of prescribers in each country will be selected. Otherwise, the sample will come from the list of neurologists who were mailed the Physician's Guide, who have not participated in the neurologist survey. Sampled prescribers will be asked to provide survey invitations to their patients being treated with TROBALT. Each prescriber will be given 10 invitations and asked to provide these invitations to up to 10 consecutive patients who have been prescribed TROBALT in the last 3 months. If the patient response rate using this recruitment method is lower than expected, then other options will be identified including patient panels where available.

Following recruitment, patients' understanding of the potential risks associated with TROBALT will be evaluated using an online survey or the same survey instrument delivered during a telephone interview. The latter option aims to accommodate individuals who are not comfortable with online technology or are not computer literate. Each invitation will include information on how to access the online survey and will also provide the toll-free number for accessing the Survey Call Centre.

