3.3.2. Measures to minimise bias in the surveys

The following are measures to minimise bias in the surveys:

- Telephone interviewers are highly trained and use a standardized script to administer interviews.
- All questions will be programmed to ensure that questions are asked in the appropriate sequence. Skip patterns will be clearly indicated. Respondents cannot go back to a question once the question has been answered and cannot skip ahead. All questions must be answered in order to complete the survey.
- Response options presented in a list will be randomized to minimize positional bias.
- Programming will be reviewed by quality control and simulated users (User Acceptance Testing) prior to implementing the survey.

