6.2. Analyses

6.2.1. Patient survey analysis

Patient demographics and indication for TROBALT use (epilepsy/ other) will be summarised using descriptive statistics for continuous data and proportions for categorical data.

The primary outcome is the proportion of patients answering each question of patient understanding of the risks associated with TROBALT correctly. Point estimates for the proportion with correct responses, and associated confidence intervals, will be calculated for each question about the risks of TROBALT. In the case of multiple choice questions, the number and proportion of patients reporting each response will also be provided.

The proportion of correct answers to survey questions will be summarised overall, and by demographic subgroups such as country. Consideration of these subgroups may highlight differences in patients' responses. Although the sample size in some subgroups may be relatively small and have low precision, data will be grouped into 2-3 sub-categories as appropriate to identify potential trends in patient understanding including:

- Demographics (gender, age, education level)
- Country
- TROBALT use (e.g., months using TROBALT, method of obtaining TROBALT (pharmacy, neurologist, mail, internet), whether the patient read the PIL)

The survey results will be presented with Germany included in the overall study population, then separately for Germany and the remaining specified European countries.

This study is descriptive; hence there will be no formal statistical testing completed.

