- 9. How did you receive your first prescription for TROBALT?
 - From my neurologist
 - From another doctor or nurse other than my neurologist
 - Other (please specify)_ [FREE TEXT]

- 10. How do you obtain your repeat prescriptions for TROBALT? (Select all that apply)
 - From a pharmacy
 - From my neurologist's office
 - From a doctor or nurse other than my neurologist
 - By postal delivery
 - Through an internet order
 - Other (please specify)_ [FREE TEXT]

- 11. For how long have you been taking TROBALT?
 - Less than 1 month
 - 1 to 3 months
 - 4 to 6 months
 - 7 to 12 months
 - More than 1 year
 - I don't know

- 12. A Patient Information Leaflet comes with TROBALT. Have you read this leaflet?
 - Yes
 - No
 - I don't know

- 13. Which of these side effects are more likely to happen with TROBALT? Answer "yes," "no" or "I don't know" for each side effect.

	Yes	No	I Don't know
--	------------	-----------	---------------------

Cannot pass urine (urinary retention)			
Diarrhea			
Being confused			
Fever			
Seeing or hearing things that are not there (hallucinations)			
Severe mental problems, such as being out of touch with reality (psychotic disorders)			

14. You should call your doctor right away if you have which of these symptoms?
Please answer “yes,” “no” or “I don’t know” for each one.

	Yes	No	I Don’t Know
Trouble starting to pass urine (urinary hesitation)			
Headache			
Thoughts of harming or killing yourself (suicidality)			
Gaining weight			
Constipation			

15. How did you learn about the possible side effects of TROBALT? Please answer “yes,” “no” or “I don’t know” for each one.

	Yes	No	I Don’t Know

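### Looking up answers during the survey is neither discouraged nor recorded in the text at hand, so the proportions correct may overstate unaided knowledge

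*Protocol*

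**What the plan says.** The objectives (Section 2) are to assess understanding of the significant risks. The primary outcome (Sections 4.3 and 4.4) is the proportion answering each risk item correctly.

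- **Mode.** Section 3.1 has patients' understanding "evaluated using an online survey or the same survey instrument delivered during a telephone interview". For the other survey, the Protocol Summary says "Neurologists will be invited to take the survey online".
- **Access to the PIL.** Section 8 says the leaflet is not supplied during the survey, "unless by chance they happen to have it with them when taking the survey". Appendix 3, Question 12, reads "A Patient Information Leaflet comes with TROBALT. Have you read this leaflet". Eligible patients are current users or filled a prescription within three months (Section 3.2.1.1).
- **Access to the Guide.** Section 1 says all neurologists in the surveyed countries were sent a letter with the Physician's Guide and SmPC at launch.
- **Inference drawn.** Section 8 concludes that "each patient's knowledge of the risks of TROBALT is based on his/her overall experience which may or may not include the PIL". Of the questions on the PIL's role it adds only "but the responses may be subject to recall bias".
- **Bias measures.** Section 3.3.2 lists scripted interviewers, fixed sequence, randomised response options and user testing. It also says "Respondents cannot go back to a question once the question has been answered and cannot skip ahead".
- **Source items.** Patient Questions 12 and 15 and neurologist Questions 25 and 26 ask about past reading and sources of information. None asks about use while answering.
- **Planned split.** Section 6.2.1 lists "whether the patient read the PIL" among the patient subgroups.

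**The concern.** A respondent who reads the leaflet or Guide while answering is scored exactly like one who knows the answer. Section 8's reasoning from past experience does not cover that respondent, and recall bias is a different problem. The instruments also point to the source: patient Question 12 names the leaflet just before the first risk item, patient Question 16 opens by citing it, and neurologist Question 18 asks what the Guide says. Many neurologist items (maximum dose, titration step, weeks, QTc action) are facts that can be checked in seconds.

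The stated goal is to judge whether the educational plan works, and the early survey is meant to allow weak messages to be revised. Look-up that yields correct answers can only raise the primary proportions, so a poorly understood message could look well understood. A larger sample does not reduce this. Information that is never collected cannot be recovered by any later analysis plan.

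**Working it through.** **1. The protocol's own precision.** Section 7 and Table 1 give ±6.0 points at 60% correct and ±4.8 at 80%, both for n = 250. The Wald half-width is 1.96 × √(p(1 − p)/n).
- p = 0.60: 1.96 × √(0.24/250) = 6.07 points, against 6.0 stated.
- p = 0.80: 1.96 × √(0.16/250) = 4.96 points, against 4.8 stated.

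The figures reproduce to within 0.2 points. They cover sampling error only.

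**2. Effect of look-up on a primary proportion.** The documents give no look-up rate, so every rate here is an assumption. Let u be the percentage correct unaided, 95 the percentage correct when looking up, and c the share who look up. Then observed = u(1 − c) + 95c, and bias = (95 − u)c.

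| c | u = 60: observed (bias) | u = 80: observed (bias) |
|---|---|---|
| 10% | 63.5 (+3.5) | 81.5 (+1.5) |
| 20% | 67.0 (+7.0) | 83.0 (+3.0) |
| 30% | 70.5 (+10.5) | 84.5 (+4.5) |

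Bias equals the stated margin at:
- u = 60: c = 6.0/35 = 17.1%.
- u = 80: c = 4.8/15 = 32%.

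**3. A second model as a check.** Suppose instead that a share f of would-be wrong answers is looked up and becomes correct. Bias is then (100 − u)f. At u = 60 it reaches 6.0 points when f = 6.0/40 = 15%, giving 66% observed. The standard error there is √(0.66 × 0.34/250) = 3.0 points, so the bias is about two standard errors. The nominal 95% interval then covers true unaided knowledge about 48% of the time. At f = 5% the bias is 2.0 points and coverage about 90%.

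**4. The PIL-read split.** Question 12 is answered before Question 13 and cannot be revisited. A non-reader who opens the leaflet for Question 13 therefore stays in the non-reader group. Assume true rates of 65% (readers) and 50% (non-readers), a gap of 15 points, and let 20% of would-be wrong answers be looked up:
- readers only: 65 + 0.20 × 35 = 72; gap 72 − 50 = 22;
- non-readers only: 50 + 0.20 × 50 = 60; gap 65 − 60 = 5;
- both groups: gap 72 − 60 = 12.

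The distortion can go either way.

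**The case against.** The strongest points on the other side, and what stands of each:

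- **Materials at hand are not established.** A reader might infer that respondents normally answer with the leaflet or Guide beside them. The protocol does not say so. The PIL is not supplied and its presence is only conceded as possible. The Guide letter template is dated May 2011 and the survey starts in November 2012. This stands: access is foreseeable, not shown.
- **Not every patient is online.** Patients may choose a scripted telephone interview. This stands, although a telephone respondent could also hold the leaflet. Mode is self-selected, since the telephone option is meant for people uncomfortable with online technology, so an online/telephone contrast would be confounded.
- **The PIL effect is not necessarily inflated.** A reader might infer that look-up exaggerates the benefit of reading the PIL. That follows only if look-up is concentrated among recorded readers; step 4 shows the gap can also shrink.
- **Part of it is disclosed.** Section 8 mentions possible PIL access, and Section 6.2.1 calls the study descriptive, without formal testing. No pass threshold is stated that look-up could wrongly satisfy. This lowers the stakes, but Section 8 does not draw the consequence for the primary proportions and omits neurologists altogether.
- **Unseen text.** Appendices 2 and 4 and the invitation letters are not in the text at hand and may ask respondents to answer from memory. This stands for the instruction. Such a text would not supply the missing questionnaire item.

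**Conclusion.** The point holds in a limited form. In the text at hand, nothing discourages or records look-up during the survey, Section 8 treats patient access to the PIL as chance despite Question 12, and the limitation is not extended to neurologists. The proportions correct may overstate unaided knowledge; the documents do not support saying that they will. On assumed rates, the bias passes the stated sampling margin at about 17% look-up when 60% would be correct unaided, but only at about 32% when 80% would be. The PIL-read split is hard to interpret, with no fixed direction of error. There is no arithmetic error in the precision table. The design can still be used, and the gap is worth closing before the survey opens because the remedy is small.

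**What to change.** 1. Before patient Question 13 and neurologist Question 6, add one line asking respondents to answer from memory, unless the invitations or Appendices 2 and 4 already do so.
2. After the last risk item (patient Question 17, neurologist Question 23), and before the correct answers are displayed, add one closed item to each questionnaire asking whether the leaflet, Guide or other information was consulted while answering.
3. In Sections 6.2.1 and 6.2.2, show each risk item for all respondents and for those reporting no look-up, and show the PIL-read split the same way. Read the second column as a sensitivity display: those who report no look-up are themselves a selected group.
4. In Section 8, replace the wording that treats access as chance, state the likely direction for the primary proportions, and extend the limitation to neurologists.

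Keep Question 12 where it is. Moved after the risk items, it would let a patient who first opened the leaflet during the survey truthfully report having read it, which puts looked-up answers in the reader group. A table by online versus telephone completion is optional and descriptive only.

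The cost is one instruction and one closed question per survey, their translation, and a few table columns. Self-reported look-up will be under-reported, so the bias is reduced rather than removed.

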9. STUDY MANAGEMENT

9.1. Ethical approval and patient consent

Survey participation is voluntary. The survey will begin with a question indicating the patient's or neurologist's agreement to participate in the survey. If the individual does not agree, the survey will be ended.

Ethics approval will be sought as required by individual countries.

9.2. Patient confidentiality

Privacy issues will be addressed and respected at each stage of the study. [REDACTED] will maintain strict confidentiality in handling all patient identification information. All data provided to GSK will be de-identified; no patient-level data or protected health information will be communicated to GSK.

9.3. Reporting of adverse events

See Section 4.5.

9.4. Study reporting and publications

The recruitment period is estimated to be 12 months from November 2012, though this could be earlier if the target number of participants is reached sooner than November 2013.

A final report will be written and submitted to European Medicines Agency (EMA) through the Periodic Safety Update Report (PSUR) in May 2014 (PSUR scheduled 29th September 2013 to 28th March 2014).

10. APPENDICES

Appendix 1 Template for the letter to prescribers including the TROBALT Physician's Guide

Physician address
Date

Dear Physician (or personalise with Dr and surname where possible)

Introducing new Trobalt (retigabine): a first-in-class potassium channel opener for the adjunctive treatment of epilepsy¹

GlaxoSmithKline is pleased to announce the recent marketing authorisation of Trobalt in (country). Trobalt is licensed for partial onset seizures with or without secondary generalisation in adults aged 18 years and above with epilepsy.¹

The approval was supported by the results of the pivotal phase III studies RESTORE 1 and 2, which showed that significantly more patients with uncontrolled epilepsy saw a reduction of 50% or more in seizure frequency compared to placebo when a 600mg/day, 900mg/day or 1200mg/day dose of Trobalt was added to their current anti-epileptic drug (AED) regimen.^{2,3}

Trobalt is a first-in-class AED that is thought to primarily target potassium channels in the brain⁴ which play a major role in seizures and in regulating neuronal function, providing a new therapeutic option for the treatment of uncontrolled epilepsy.^{5,6}

To date, 45 studies investigating Trobalt (phase I, II and III) have been completed evaluating more than 2,000 subjects, including 1,365 patients with epilepsy.⁷

Trobalt has been shown to be generally tolerated with most reported adverse events being transitory, mild to moderate in severity and occurring early during the titration period. Very common side effects were dose-related and included dizziness, somnolence and fatigue¹

AEDs may have specific considerations to ensure appropriate prescribing. With Trobalt, the following advice should be discussed with your patients before initiating therapy.

Trobalt must be taken orally, with or without food, in three divided daily doses. Tablets should be swallowed whole and not chewed, crushed or divided. Trobalt must be titrated to reach an effective dose. The starting dose is 300 mg/day, increased by 150 mg/day weekly according to patient response and tolerability. The maximum total daily dose is 1200 mg/day.¹

Treatment initiation packs are available for patients using the standard dose titration regimen to facilitate the first 2 weeks of therapy, and reach a potentially therapeutic dose of 600 mg/day by the third week of therapy.

Appropriate dose titration may minimise the risk of central nervous system-related adverse events, including hallucination and psychotic disorders.

Date of preparation: May 2011
NECE/RTG/0033/11

Prescribing Information is available on the back page

Trobalt™
retigabine tablets

1. Urinary effects

Urinary retention, dysuria and urinary hesitation were reported in controlled clinical studies with Trobalt, generally within the first 8 weeks of treatment. Trobalt must be used with caution in patients at risk of urinary retention, and it is recommended that patients are advised about the risk of these possible effects.¹

Does your patient have symptoms of urinary retention e.g. hesitancy, poor stream?

Does your patient take drugs that can cause urinary retention e.g. anticholinergics?

Is your patient able to communicate new symptoms of urinary retention?

2. QT interval prolongation

A study of cardiac conduction in healthy subjects has demonstrated that Trobalt titrated to 1200 mg/day produced a QT prolonging effect. A mean increase in Individual Corrected QT Interval (QTcI) of up to 6.7 ms (upper bound of 95% one-sided CI 12.6 ms) was observed within 3 hours of dosing.¹

Caution should be taken when Trobalt is prescribed with medicinal products known to increase QT interval and in patients with known prolonged QT interval, congestive cardiac failure, ventricular hypertrophy, hypokalaemia or hypomagnesaemia and in patients initiating treatment who are 65 years of age and above.¹

In these patients it is recommended that an electrocardiogram (ECG) is recorded before initiation of treatment with Trobalt and in those with a corrected QT interval >440 ms at baseline, an ECG should be recorded on reaching the maintenance dose.¹

Does your patient have a history of cardiac disease?

Does your patient take drugs that are known to cause QT prolongation?

Retigabine has not been shown to cause cardiac arrhythmias in the randomised clinical trials, however patients should be advised to report new symptoms that might indicate a prolonged QT interval, for example palpitations, syncope.

3. Psychiatric effects

During controlled clinical studies, confusional state, psychotic disorders and hallucinations were reported, generally within the first 8 weeks of treatment. It is recommended that patients are

Date of preparation: May 2011
NECE/RTG/0033/11

Trobalt™
retigabine tablets

advised about the risk of these possible effects and to not exceed the recommended titration schedule. ¹

For further information please contact (country to insert specific details)

Yours faithfully,

Xxxxxxx
(Title)

References

1. Trobalt Summary of Product Characteristics. GlaxoSmithKline; 2011.
2. Brodie MJ *et al.* Efficacy and safety of adjunctive retigabine in refractory partial epilepsy. *Neurology* 2010; **75**: 1817-1824.
3. GlaxoSmithKline Data on File. (French *et al.*)
4. Main MJ *et al.* Modulation of KCNQ2/3 potassium channels by the novel anticonvulsant retigabine. *Mol Pharmacol* 2000; **58**: 253-262.
6. Rogawski M. KCNQ2/KCNQ3 K+ channels and the molecular pathogenesis of epilepsy: implications for therapy. *Trends Neurosci* 2000; **23**: 393-398.
7. GlaxoSmithKline Data on File. (Advisory Committee Briefing document).

Insert local PI

Date of preparation: May 2011
NECE/RTG/0033/11

Trobalt™
retigabine tablets

Appendix 3 Questionnaire for Patients Prescribed TROBALT Who are Recruited by Invitation Letter through their Healthcare Professional

[Use for both Web-based and telephone survey]

Screening Questions:

1. Do you agree to take part in this survey?
 - **Yes**
 - No (Exclude)

2. Are you now taking TROBALT or did you take TROBALT within the past 3 months?
 - **Yes**
 - No (Exclude)

3. When was the last time that you filled a prescription for TROBALT?
 - Less than 1 month ago (OK)
 - Between 1-2 months ago (OK)
 - Between 2-3 months ago (OK)
 - More than 3 months ago (Exclude)
 - I do not know (Exclude)

4. What is your current age?
 - Under age 18 (Exclude)
 - 18-20 years
 - 21-30 years
 - 31-40 years
 - 41-50 years
 - 51-60 years
 - 61-70 years
 - Over age 70

5. Do you currently work for GlaxoSmithKline or [REDACTED] Corporation?
 - Yes (Exclude)
 - **No**

Questionnaire for Patients Prescribed TROBALT:

6. What is the reason you take TROBALT? (Select all that apply)
 - To treat my epilepsy (SKIP to Q #8)
 - To treat my headaches
 - To treat my heartburn
 - Other (please specify) [FREE TEXT]
 - I do not know

- 7. Do you take prescription medicine to treat epilepsy?
 - Yes
 - No (**SKIP to Q #9**)
 - I don't know (**If this response chosen, please skip to Q#9**)

- 8. How many prescription medicines for epilepsy do you take?
 - 1
 - 2
 - 3
 - 4 or more
 - None

- 9. How did you receive your first prescription for TROBALT?
 - From my neurologist
 - From another doctor or nurse other than my neurologist
 - Other (please specify)_ [FREE TEXT]

- 10. How do you obtain your repeat prescriptions for TROBALT? (Select all that apply)
 - From a pharmacy
 - From my neurologist's office
 - From a doctor or nurse other than my neurologist
 - By postal delivery
 - Through an internet order
 - Other (please specify)_ [FREE TEXT]

- 11. For how long have you been taking TROBALT?
 - Less than 1 month
 - 1 to 3 months
 - 4 to 6 months
 - 7 to 12 months
 - More than 1 year
 - I don't know

- 12. A Patient Information Leaflet comes with TROBALT. Have you read this leaflet?
 - Yes
 - No
 - I don't know

- 13. Which of these side effects are more likely to happen with TROBALT? Answer "yes," "no" or "I don't know" for each side effect.

	Yes	No	I Don't know
--	------------	-----------	---------------------

Cannot pass urine (urinary retention)			
Diarrhea			
Being confused			
Fever			
Seeing or hearing things that are not there (hallucinations)			
Severe mental problems, such as being out of touch with reality (psychotic disorders)			

14. You should call your doctor right away if you have which of these symptoms?
Please answer “yes,” “no” or “I don’t know” for each one.

	Yes	No	I Don’t Know
Trouble starting to pass urine (urinary hesitation)			
Headache			
Thoughts of harming or killing yourself (suicidality)			
Gaining weight			
Constipation			

15. How did you learn about the possible side effects of TROBALT? Please answer “yes,” “no” or “I don’t know” for each one.

	Yes	No	I Don’t Know
Neurologist told me			
Family doctor or general practitioner (GP) told me			
Online			
Patient Information Leaflet			
Patient Support Group			

16. The Patient Information Leaflet says TROBALT can cause heart problems. Which one of the following heart conditions can TROBALT cause? (Select one answer)

- Chest pain
- **Making my heart beat too fast or too slow**
- Heart attack
- All of the above
- None of the above

17. Which of the following raises the chance for effects on heart rhythm when you take TROBALT? Please answer “yes,” “no” or “I don’t know” for each one.

	Yes	No	I Don’t Know
Taking other medicines	X	O	O
Smoking	O	X	O
Already having a heart problem	X	O	O
Having asthma	O	X	O
Being 65 years old or older	X	O	O

18. In what country do you live? (Will have drop-down menu of all countries in the survey).

19. What is your gender?

- Male
- Female

20. What is the highest level of education you have completed?

- Some secondary school (EU equivalent) or less
- Finished secondary school
- Some university or technical/trade school
- Graduated university
- Post graduate studies
- Prefer not to answer

[CLOSING] Thank you for completing the survey. The following are the correct answers to the survey questions about TROBALT.

The following are the correct answers to the survey questions about TROBALT.

Which side effects are more likely to happen with TROBALT?

- Cannot pass urine (urinary retention)
- Being confused
- Seeing or hearing things that are not there (hallucinations)
- Severe mental problems, such as being out of touch with reality (psychotic disorders)

You should call your doctor right away if you have which symptoms?

- Trouble starting to pass urine (urinary retention)
- Thoughts of harming or killing yourself (suicidality)

The Patient Information Leaflet says TROBALT can cause heart problems. Which heart condition can TROBALT cause?

- Making my heart beat too fast or too slow

Which factors raise the chance for effects on heart rhythm when you take TROBALT?

- Taking other medicines
- Already having a heart problem
- Being 65 years old or older

The information in this survey and the Patient Information Leaflet (PIL) should not take the place of talking with your health care professional. If you have any questions about your condition or treatment, or if you would like more information about TROBALT, talk to your health care professional. The Patient Information Leaflet can be obtained from the following website: <http://www.gsk.com/products/prescription-medicines/trobalt.htm>.

Thank You

Appendix 5 Questionnaire for Neurologists who Prescribe AEDs and were Sent the TROBALT Letter Containing the Physician's GuideScreening Questions:

1. Do you agree to take part in this survey?
 - **Yes**
 - No (Exclude)

2. When was the last time you prescribed an anti-epileptic drug for a patient?
 - **Less than a month ago**
 - Between 1 and 2 months ago
 - Between 2 and 3 months ago
 - More than 3 months ago (Exclude)

3. Have you ever prescribed TROBALT?
 - **Yes**
 - No
 - I don't know

4. In which country is your primary medical practice?
 - **Germany**
 - Denmark
 - United Kingdom
 - Switzerland
 - Sweden
 - Spain
 - Slovakia
 - Norway
 - Other (exclude)

[QUOTAS WILL BE ESTABLISHED FOR 200 NEUROLOGISTS FROM UK, SWEDEN, DENMARK, SWITZERLAND, SPAIN, SLOVAKIA, AND NORWAY; AT LEAST 75 SHOULD HAVE PRESCRIBED TORBALT. QUOTA OF 100 NEUROLOGISTS FROM GERMANY, OF WHICH AT LEAST 50 SHOULD HAVE PRESCRIBED TROBALT.]

5. Are you an employee of GlaxoSmithKline or [REDACTED] Corporation?
 - **Yes (Exclude)**
 - **No**

Questionnaire for Neurologists who Prescribe AEDs and Were Sent the TROBALT Letter Containing the Physician's Guide

[CORRECT ANSWERS ARE INDICATED IN BOLD]

6. For which of the following conditions is TROBALT approved for use?
- Migraine
 - **Partial-onset seizures**
 - All types of seizures
 - All of the above
 - None of the above
 - I don't know
7. Is TROBALT indicated for use as monotherapy?
- Yes
 - **No**
 - I don't know
8. What is the maximum recommended daily maintenance dose of TROBALT for most patients? (Please select the best response.)
- 600 mg
 - 900 mg
 - **1200 mg**
 - 2000 mg
 - None of the above
 - I don't know
9. Which one of the following statements is true? (Please select the best response.)
- TROBALT should be taken once a day.
 - TROBALT should be taken twice a day.
 - **TROBALT should be taken three times a day.**
 - TROBALT should be taken four times a day.
 - None of the above
 - I don't know
10. When increasing the dose, what is the maximum total daily dose at which TROBALT can be increased once every 7 days? (Please select the best response.)
- 50 mg
 - **150 mg**
 - 300 mg
 - 600 mg
 - None of the above
11. Which one of the following statements is true? (Please select the best response.)
- There are no lower age limits for TROBALT usage.
 - The youngest age at which TROBALT can be used is 12.
 - **The youngest age at which TROBALT can be used is 18.**
 - I don't know

Please respond “true,” “false” or “I don’t know” to each of the following questions:

12. The quickest time by which the minimum maintenance dose of 600mg should be reached is the third week?
- **True**
 - False
 - I don’t know
13. For the general population, the recommended total initial dosage should be 150mg per day for one week.
- True
 - **False**
 - I don’t know
14. People taking TROBALT had a higher chance of experiencing which of the following risks in clinical studies? (Please select all that apply)
- **Urinary retention**
 - **Confusional state**
 - **Hallucinations**
 - **Psychotic disorders**
 - Myocardial infarction
 - Renal carcinoma
 - All of the above
 - None of the above
 - I don’t know
15. It is known from controlled studies that adverse events related to voiding dysfunction generally tend to be reported how soon after starting TROBALT?
- Within the first week
 - **Within the first 8 weeks**
 - After 4 months
 - After 12 months
 - I don’t know
16. It is known from controlled studies that confusional state, hallucinations, and/or psychotic disorders generally tend to be reported how soon after starting TROBALT?
- 4 weeks
 - **8 weeks**
 - 12 weeks
 - 16 weeks
 - I don’t know

17. Which of the following urinary symptoms, if any, should you specifically advise patients taking TROBALT to watch out for? (Please select the best response.)
- Pain when urinating
 - Difficulty starting urination
 - Slow stream
 - Inability to pass urine
 - **All of the above**
 - None of the above
 - I don't know
18. According to the TROBALT Physician's Guide, appropriate dose titration may minimize the risk of which of the following adverse events? (Please select the best response.)
- QT prolongation
 - **CNS side effects such as hallucinations**
 - Urinary retention
 - All of the above
 - None of the above
 - I don't know

[DO NOT DISPLAY QUESTIONS 19 and 20 FOR RESPONDENTS FROM SWITZERLAND]

19. Using the Treatment Initiation Pack, by which week can the patient reach a dose of 600mg/day?
- 2 weeks
 - **3 weeks**
 - 4 weeks
 - 5 weeks
 - None of the above
20. At what dose has TROBALT been shown to produce a possible QT prolonging effect?
- 600 mg
 - 900 mg
 - **1200mg**
 - 1800 mg
 - I don't know
21. For which patients is it recommended that an ECG is recorded before initiating TROBALT? (Please select all that apply.)
- Patients with hypertension
 - **Patients with congestive heart failure**
 - **Patients with ventricular hypertrophy**

- **Patients with hypokalemia**
 - All of the above
 - None of the above
 - I don't know
22. What should you do in a patient with a QTc of **more** than 440ms before starting TROBALT? (Please select the best response)
- Recheck the ECG 1 week after the first dose
 - Recheck the ECG at monthly intervals
 - **Recheck the ECG after reaching the maintenance dose**
 - I don't know
23. Which new cardiac effects in particular should you warn your patients about after prescribing TROBALT? (Please select all that apply)
- Syncope
 - Palpitations
 - Any other symptoms of arrhythmia
 - **All of above**
 - None of the above
24. How would you classify your primary medical specialty?
- Neurology
 - Neurosurgery
 - Epileptology
 - Other (specify) _____ [FREE TEXT]
 -
25. Have you read the TROBALT information letter that was sent at the launch of TROBALT?
- Yes
 - No
 - I don't know
26. From which of the following sources have you learned about the risks associated with use of TROBALT? (Please select all that apply)
- TROBALT launch letter
 - GlaxoSmithKline medical information
 - Other health care professionals
 - GlaxoSmithKline promotional materials
 - GlaxoSmithKline sales representatives
 - Journal article
 - GlaxoSmithKline-sponsored educational meeting
 - None of the above

27. What is your gender?

- Male
- Female

28. For how many years have you been in medical practice?

- Less than 3 years
- 3-5 years
- 6-10 years
- 11-15 years
- 16-20 years
- More than 20 years
- Prefer not to answer

29. Do you agree to provide your name and address so that we can issue a payment for your time in completing this survey?

- Yes (Record name and address)
- No

Name _____

Address _____

[CLOSING] That ends the survey. Thank you again for your help. The correct answers to the questions about TROBALT follow.

The following are the correct answers to the survey questions about TROBALT.

For which condition is TROBALT approved for use?

